9.3.4 Thromboembolic events

Cancer patients are at increased risk of venous thromboembolic events. DVT and pulmonary embolism have been observed in clinical studies with cabozantinib, including fatal events. Subjects who develop a pulmonary embolism and/or DVT should have their study treatment interrupted until therapeutic anticoagulation is established. Treatment with cabozantinib may be resumed in subjects with DVT or pulmonary embolism if it is determined that the event is uncomplicated, the patient is relatively asymptomatic, and anticoagulation does not place them at a significant risk per discretion of the investigator.

LMWHs are the preferred management for thrombotic events. Oral anticoagulants (e.g. warfarin or other coumarin-related agents, direct thrombin or direct FXa inhibitors, antiplatelet agents, or chronic use of aspirin above low dose levels for cardioprotection per local applicable guidelines) are not allowed.

Arterial thrombotic events (e.g. TIA, MI) have been observed in studies with cabozantinib. Further treatment with cabozantinib should be discontinued in subjects who develop an acute MI, cerebral infarction, or any other clinically significant arterial thromboembolic complication.

9.3.5 Hypertension

BP should be monitored in a sitting position in a relaxed setting. Decisions to reduce or interrupt the dose of study treatment must be based on BP readings taken by an experienced health care provider and must be confirmed with a second measurement at least 5 minutes following the first measurement.

Cabozantinib should be discontinued in subjects with hypertensive emergency.

The management of hypertension related to cabozantinib is outlined in Table 9.3.5.1.

Table 9.3.5.1. Management of hypertension associated with cabozantinib	
Criteria for dose modification	Management and cabozantinib modification
Subjects NOT receiving optimized anti-hypertensive therapy	
> 150 mm Hg (systolic) ^a and < 160 mm Hg OR > 100 mm Hg (diastolic) and < 110 mm Hg	
 Optimize antihypertensive medications by adding new antihypertensive medications and/or increase the dose of existing medications. Reduce cabozantinib treatment by one dose level if optimal antihypertensive therapy (usually to include 3 agents) does not result in BP <150 mm Hg systolic or <100 mm Hg diastolic. If subject is symptomatic, interrupt cabozantinib treatment and resume once BP <150 mm Hg systolic or <100 mm Hg diastolic and symptoms resolve.
≥ 160 mm Hg (systolic) OR ≥ 110 mm Hg (diastolic)	
 Reduce cabozantinib by one dose level^b or interrupt cabozantinib treatment per investigator discretion. Add new anti-hypertensive medications and/or increase the dose of existing medications. If optimized antihypertensive therapy (usually to include 3 agents) does not result in BP < 150 mm Hg systolic or < 100 mm Hg diastolic, cabozantinib treatment should be interrupted and resumed at dose reduction (if not already done) when BP <150 mm Hg systolic or <100 mm Hg diastolic. Cabozantinib treatment should be interrupted if upper limits of systolic BP (≥ 160 mm Hg) are sustained and not adequately manageable, if systolic BP is > 180 mm Hg or diastolic BP > 110 mm Hg, or if subject is symptomatic. Re-start cabozantinib treatment at the most tolerable dose and re-escalate only if BP falls to and is sustained at < 150 mm Hg systolic and < 100 mm Hg diastolic.
Hypertensive emergency ^c	
 Discontinue cabozantinib treatment.

BP, blood pressure.

^aThe investigator may decide to initiate or adjust antihypertensive treatment at a lower threshold than systolic BP >150 or diastolic BP >100 based on their clinical judgment and assessment of the individual subject.

^bPermitted dose levels are defined in Section 9.4.

^cHypertensive emergency is defined as uncontrolled elevated BP with clinical evidence of progressive or impending end-organ damage (e.g. myocardial infarction/ischemia, intracranial hemorrhage, cerebral ischemia, pulmonary edema, encephalopathy, kidney damage).

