9.3 Information on cabozantinib toxicity

AEs may occur within the first few weeks after starting cabozantinib (steady state reached at approximately 2 weeks). Cabozantinib-related AEs that generally have an early onset include hypocalcemia, hypokalemia, thrombocytopenia, hypertension, PPES, abdominal pain, mucosal inflammation, constipation, diarrhea, and vomiting.

AEs should be managed with supportive care at the earliest signs of toxicity. In all subjects, dose delays and reductions of cabozantinib to manage toxicity are allowed under the guidelines below. In general, grade 3 cabozantinib-related AEs require dose interruption until AEs recover to grade 1, at which point treatment may be resumed at the next lower dose. Moreover, dose reductions are recommended for

grade 2 events that, if persistent, could become serious and/or intolerable. **If cabozantinib is delayed by more than 4 weeks, it must be discontinued**, unless there is reason to believe that the patient will benefit from resuming cabozantinib. In this case, resuming cabozantinib at dose reduction must be discussed with the PI.

Furthermore, cabozantinib should be discontinued for the following AEs: visceral perforation or fistula formation, severe hemorrhage, serious arterial thromboembolic events, nephrotic syndrome, hypertensive emergency, persistent uncontrolled hypertension despite optimal medical management, and RPLS.

If an AE is believed to be probably/definitely related to cabozantinib, and not related to pembrolizumab, then pembrolizumab may be continued even if cabozantinib needs to be interrupted or discontinued, as long as pembrolizumab is not expected to delay recovery or worsen the AE.

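### Table 9.3.5.1 states blood-pressure control with 'or', so a row 1 patient with only one raised pressure can be read as already controlled

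*Combined protocol and SAP*

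**What the plan says.** Table 9.3.5.1 is entered on either pressure. Row 1 covers systolic above 150 and below 160, or diastolic above 100 and below 110. Row 2 covers systolic of 160 or more, or diastolic of 110 or more.

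Control is then stated five times:

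- Row 1, reduction: antihypertensives are optimized, and cabozantinib goes down one level if optimal therapy "does not result in BP <150 mm Hg systolic or <100 mm Hg diastolic".
- Row 1, hold for symptoms: treatment is interrupted, then "resume once BP <150 mm Hg systolic or <100 mm Hg diastolic and symptoms resolve". No resumption dose is stated.
- Row 2, failure of optimized therapy: if it "does not result in BP < 150 mm Hg systolic or < 100 mm Hg diastolic, cabozantinib treatment should be interrupted".
- Row 2, resumption after that interruption: "resumed at dose reduction (if not already done) when BP <150 mm Hg systolic or <100 mm Hg diastolic".
- Row 2, closing sentence (after a clause on which dose to restart with): "re-escalate only if BP falls to and is sustained at < 150 mm Hg systolic and < 100 mm Hg diastolic".

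The first four use *or*; the last uses *and*. Row 2 also has separate grounds for interruption: systolic values of 160 or more that "are sustained and not adequately manageable", systolic above 180, diastolic above 110, or symptoms.

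Elsewhere, exclusion criterion 17.a.ii (Section 5.2 and the synopsis) counts hypertension as uncontrolled when sustained pressure on optimal treatment is above 150 systolic or above 95 diastolic. Section 9.3 lists persistent uncontrolled hypertension on optimal management among the reasons to stop cabozantinib.

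**The concern.** A rule entered on either pressure should be left only when both are acceptable. Here the entry condition and the control condition use the same conjunction, so a patient can satisfy both at once. A patient with isolated systolic or isolated diastolic hypertension then counts, on the literal words, as controlled on entering row 1. The reduction bullet would never apply to that patient, and the pressure part of the resumption bullet would be met before anything had changed.

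What is at stake is cabozantinib exposure in patients whose raised pressure persists on optimal therapy. Hypertension is an expected toxicity. In the Phase 3 trial of cabozantinib after sorafenib (60 mg start), Section 1.4.1.5 reports it in 29% of patients, and at grade 3-4 in 16%. The starting dose here is 40 mg and the drug is given in combination, so those rates show only that the table is likely to be used.

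**Working it through.** No published figure needs reproducing; the check is one of logic. Write S for systolic and D for diastolic pressure, in whole mm Hg.

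**Inputs (Table 9.3.5.1).** Row 1 entry: 150 < S < 160 or 100 < D < 110. Limits for control: 150 systolic, 100 diastolic. The reduction trigger is *not controlled*; the pressure part of resumption is *controlled*.

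**Three readings of controlled.**

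- Literal: S < 150 or D < 100. Its negation, the reduction trigger, is S ≥ 150 and D ≥ 100.
- Whichever qualified: each pressure that met row entry is now below its own limit.
- Both: S < 150 and D < 100. Its negation is S ≥ 150 or D ≥ 100.

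**Results for patients on optimal therapy (reduce? / pressure part of resumption met?).**

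| Pressure | Literal | Whichever qualified | Both |
|---|---|---|---|
| 155/90 | no / yes | yes / no | yes / no |
| 140/105 | no / yes | yes / no | yes / no |
| 155/105 | yes / no | yes / no | yes / no |

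**How far the gap extends in row 1.** Take S from 110 to 159 and D from 60 to 109.

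- S 151-159 with D 60-99: 9 × 40 = 360 pairs. The trigger fires for 0 under the literal reading and for 360 under each of the others.
- D 101-109 with S 110-149: 9 × 40 = 360 pairs. Again 0, 360 and 360.
- Both raised: 9 × 9 = 81 pairs. The trigger fires for all 81 under every reading.

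The 360s depend on where the grid starts. The all-or-nothing pattern does not.

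**Order of operations in row 1 resumption.** The clause has the form A or B and symptoms resolved. If *and* binds first, it means A or (B and symptoms resolved). A patient at 140/105 then meets A (S < 150) and could resume while still symptomatic.

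**Row 2.** The *or* criterion also passes 165/90, 185/95 and 140/112; the *and* criterion fails all three. Entry to row 2 already calls for a reduction or an interruption, however. The separate triggers catch 185/95 (systolic above 180) and 140/112 (diastolic above 110), and catch 165/90 if it is sustained and unmanageable. Resumption after failed optimized therapy is at a reduced dose. The practical gap is therefore mainly in row 1.

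**Comparison with the eligibility rule.** Sustained on optimal treatment, 155/90 has S > 150 and 140/105 has D > 95. Both are uncontrolled under criterion 17.a.ii and bar entry. Under the literal reading of row 1, both count as controlled once the patient is on treatment.

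**The case against.** The strongest reply is that the literal reading defeats the row. If 155/90 is controlled on entry, the reduction and resumption bullets do nothing for any patient with one raised pressure, and no drafter intends that. The ordinary sense is that the control phrase mirrors the entry phrase: whichever pressure qualified must fall. This has force, and that reading is safe. But it shows what was probably meant, not what is written, and the printed rule still supports two opposite dosing decisions.

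Other provisions also limit the harm:

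- Row 1 requires antihypertensives to be optimized for every patient in it. What could be missed is the cabozantinib reduction, not treatment of the pressure.
- Sections 9.2 and 9.5 make the dosing instructions guidance, subject to the investigator's judgement. Footnote a allows antihypertensives at lower thresholds, but it does not address cabozantinib dose or resumption.
- Section 9.3 recommends reduction for "grade 2 events that, if persistent, could become serious and/or intolerable" and says that grade 3 events "require dose interruption until AEs recover to grade 1, at which point treatment may be resumed at the next lower dose". These routes depend on CTCAE grade, and the documents give no pressure cut-offs for the grades.
- Section 9.3 also calls for stopping cabozantinib for persistent uncontrolled hypertension. A reader might infer that every backstop in that section depends on grade; this one does not. It could reach a persistent 155/90 with a stronger action than reduction. However, Section 9.3 neither defines uncontrolled nor refers to criterion 17.a.ii.

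A reader might also infer that row 2 contradicts itself. The documents do not establish that. The *and* in the closing sentence attaches most naturally to re-escalation, and a stricter condition for raising the dose than for resuming at a reduced one can be deliberate.

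**Conclusion.** The point holds as a minor safety-wording correction. Four of the table's five control statements use *or*. On the literal reading, row 1 never triggers a reduction when one pressure is raised and the other is below its limit (systolic 151-159 with diastolic below 100, or diastolic 101-109 with systolic below 150). The safe reading always triggers it if the pressure persists on optimal therapy. The mitigations reduce the consequence without correcting the rule. Criterion 17.a.ii, which treats either raised pressure as uncontrolled, supports requiring both to be controlled, although its diastolic limit is 95 rather than 100 and it sits in the eligibility section.

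Two stronger inferences are not supported. One is that such patients would resume at an unchanged dose: row 1 states no resumption dose, so all that follows is that the pressure may still be raised. The other is that an identifiable number of patients would be affected: the documents do not give the frequency of isolated systolic or diastolic hypertension, and the grid tests logic rather than describing a population. Sample size, error rates and the primary endpoint are unaffected.

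**What to change.** Replace *or* with *and*, so that control means systolic below 150 and diastolic below 100, in four places: the row 1 reduction bullet, the row 1 symptomatic-resumption bullet, and the interruption and resumption clauses of row 2's third bullet. In the two negated clauses, add the word *both* so that failure on either pressure counts as failure. Row 1 resumption would then read: systolic <150 and diastolic <100, and symptoms resolved. That also removes the doubt about whether symptoms must resolve in every case.

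The edit is confined to one table. Its clinical cost is somewhat more dose reductions or longer holds for patients with isolated systolic or diastolic hypertension, which is what an either-pressure entry rule implies. The row 1 resumption dose could be stated in the same amendment, but that is a separate clinical choice.

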9.3.6 Stomatitis and mucositis

Preventive measures before study treatment are recommended, such as modification of ill-fitting dentures and appropriate care of gingivitis. During treatment with cabozantinib, good oral hygiene and standard local treatments such as gentle cleansing and oral rinses (e.g. with a weak solution of salt and baking soda) should be maintained. Lips should be kept moisturized with lip balm. The use of lipstick, lip-gloss, and Vaseline should be avoided.

Local treatment should be instituted at the earliest onset of symptoms. Obtain bacterial/viral culture if oral infection is suspected and treat infection as clinically indicated.

Cabozantinib should be interrupted for drug-related grade 3 stomatitis and mucositis until symptoms improve to grade 1, followed by resumption of drug at the next lower dose.

9.3.7 Skin and Subcutaneous Tissue Disorders

Wound healing and surgery: Cabozantinib has the potential to cause wound healing complications and wound dehiscence, which may even occur long after a wound has been considered healed. Therefore, surgical and traumatic wounds must not only be completely healed prior to starting cabozantinib treatment, but must also be monitored for wound dehiscence, wound infection, and other signs of impaired wound healing while the subject is being treated with cabozantinib. If dehiscence occurs, cabozantinib treatment should not be restarted until complete healing has taken place.

Treatment with cabozantinib should be stopped at least 28 days prior to scheduled surgery. The decision to resume treatment with cabozantinib after surgery should be based on clinical judgment of adequate wound healing.

Palmar-plantar erythrodysesthesia syndrome (PPES; also known as hand-foot syndrome): skin rash (including blister, erythematous rash, macular rash, skin exfoliation, dermatitis acneiform, and papular rash), pruritus, dry skin, erythema, pigmentary changes, and alopecia have been reported with cabozantinib. All subjects on study should be advised on prophylactic measures including the use of emollients, removal of calluses, avoidance of exposure of hands and feet to hot water leading to vasodilatation, protection of pressure-sensitive areas of hands and feet, and use of cotton gloves and socks to prevent injury and keep the palms and soles dry.

Early manifestations include tingling, numbness, mild hyperkeratosis, and symmetrical red and swollen areas on the palms and soles. The lateral sides of the fingers or periungual zones may also be affected. Adequate interventions are required to prevent worsening of skin symptoms such as blisters, desquamations, ulcerations, or necrosis of affected areas. Analgesics may be required for pain control. Aggressive management of symptoms is recommended. **Recommendations for treatment of PPES and dose modification of cabozantinib are summarized in Table 9.3.7.1.**

For other skin toxicities, including possible immune-mediated skin rash, please see Section 9.5.4.

Table 9.3.7.1. Management of hand-foot syndrome (PPES) associated with cabozantinib	
Grade per CTCAE v5	Management and cabozantinib modification
Grade 1: Minimal skin changes or dermatitis (e.g. erythema, edema, or hyperkeratosis without pain)	Cabozantinib treatment should be continued at the current dose. Start urea 20% cream twice daily and consider mild-moderate potency steroid topical.. If PPES worsens at any time or does not improve after 2 weeks, proceed to the intervention guidelines for Grade 2.
Grade 2: Skin changes (e.g. peeling, blisters, bleeding, fissures, edema, or hyperkeratosis) with	Cabozantinib treatment may be continued at same dose, dose-reduced, and/or interrupted at the discretion of the treating investigator depending on the degree of symptoms. Continue urea 20% cream twice daily AND add a high potency steroid topical, and add analgesics for pain control if needed. If PPES worsens or affects self-care, proceed to the intervention guidelines for

pain; limiting instrumental ADL	Grade 3.
Grade 3: Severe skin changes (e.g. peeling, blisters, bleeding, fissures, edema, or hyperkeratosis) with pain; limiting self-care ADL	Interrupt cabozantinib treatment until severity decreases to Grade 1. Continue treatment of skin reaction with high potency steroid cream and analgesics. Resume study drug at a reduced dose if PPES recovers to Grade ≤ 1 . Discontinue subject from study treatment if PPES does not improve within 4 weeks.

CTCAE, Common Terminology Criteria for Adverse Events; NSAID, non-steroidal anti-inflammatory drug; PPES, palmar plantar erythrodysesthesia syndrome.

¹Permitted dose levels are defined in Section 9.4.

9.3.8 Osteonecrosis

Osteonecrosis has been reported in subjects treated with cabozantinib. Additional risk factors include use of bisphosphonates and denosumab, chemotherapy and anti-angiogenic drugs, use of corticosteroids, local radiotherapy, and dental or orofacial surgery procedures.

Osteonecrosis of the jaw (ONJ) can manifest as jaw pain, osteomyelitis, osteitis, bone erosion, tooth or periodontal infection, toothache, gingival ulceration, or gingival erosion. Persistent pain or slow healing of the mouth or jaw after dental surgery may also be manifestations of osteonecrosis.

Perform an oral examination prior to initiation of cabozantinib and periodically during cabozantinib treatment. Advise subjects regarding oral hygiene practice and to quickly report symptoms to Investigator. Caution should be used in subjects receiving bisphosphonates.

Dental surgery or invasive dental procedures should be avoided. In cases where dental procedures are unavoidable, treatment with cabozantinib should be interrupted for at least 4 weeks prior to the procedure and resumed after complete wound healing has occurred. Bone healing may often require a protracted time.

Withhold cabozantinib for development of ONJ until complete resolution.

9.3.9 Proteinuria

Proteinuria has been reported with cabozantinib. Proteinuria should be monitored by measuring UPCR once every 6 weeks (every 2 cycles) on treatment, and more frequently if abnormal. **Table 9.3.9.1 provides treatment guidelines for proteinuria related to cabozantinib.**

Cabozantinib should be discontinued in subjects who develop nephrotic syndrome (proteinuria > 3.5 grams per day in combination with low blood protein levels, high cholesterol levels, high triglyceride levels, and edema).

Table 9.3.9.1. Management of proteinuria associated with cabozantinib	
Severity of proteinuria (UPCR)	Management and cabozantinib modification
≤ 1 mg/mg (≤ 113.1 mg/mmol)	
 • No change in cabozantinib treatment or monitoring.
> 1 and < 3.5 mg/mg (> 113.1 and < 395.9 mg/mmol)	
 • Consider confirming with a 24-h protein assessment within 7 days. • No change in cabozantinib treatment required if UPCR ≤ 2 mg/mg or urine protein ≤ 2 g/24 h on 24-h urine collection. • Dose reduce or interrupt cabozantinib treatment if UPCR > 2 mg/mg on repeat UPCR testing or urine protein > 2 g/24 h on 24-h urine collection. Continue cabozantinib on a reduced dose if UPCR decreases to < 2 mg/mg. Consider interrupting cabozantinib treatment if UPCR remains > 2 mg/mg despite a dose reduction until UPCR decreases to < 2 mg/mg. Restart cabozantinib treatment at a reduced dose after a dose interruption. • After dose reduction or interruption, repeat UPCR within 7 days and once per week. If UPCR < 1 mg/mg on 2 consecutive readings, UPCR monitoring can revert to once monthly. (Second reading is confirmatory and can be done within 1 week of first reading.) If UPCR remains > 1 mg/mg and < 2 mg/mg for 1 month or is determined to be stable (< 20% change) for 1 month, check urine protein/creatinine once monthly as clinically indicated.
≥ 3.5 mg/mg (≥ 395.9 mg/mmol)	
 • Interrupt cabozantinib treatment pending repeat UPCR within 7 days and/or 24-h urine protein. • If ≥ 3.5 mg/mg on repeat UPCR, continue to interrupt cabozantinib treatment and check UPCR every 7 days. If UPCR decreases to < 2 mg/mg, restart cabozantinib treatment at a reduced dose and monitoring of urine protein/creatinine should continue weekly until the UPCR decreases to < 1 mg/mg. If UPCR remains > 1 mg/mg and < 2 mg/mg for 1 month or is determined to be stable (< 20% change) for 1 month, check urine protein/creatinine once monthly or as clinically indicated.
Nephrotic syndrome	
 • Discontinue cabozantinib.

RCC, renal cell carcinoma; UC, urothelial carcinoma; UPCR, urine protein/creatinine ratio.

9.3.10 Nervous system disorders

Cabozantinib appears to represent minimal risk of adverse neurological effects based on nonclinical Good Laboratory Practice (GLP)-compliant toxicology studies. Dysphonia, dysgeusia, headache, dizziness, confusional state, convulsion, depression, memory impairment, hypoesthesia, peripheral neuropathy, insomnia, ataxia, and encephalopathy have been observed in clinical studies with cabozantinib. The development of any new or progressive, unexplained neurological symptoms should be assessed for underlying causes.

RPLS has been reported. RPLS should be considered in any subject presenting with seizures, headache, visual disturbances, confusion or altered mental function. Cabozantinib treatment should be discontinued in subjects with RPLS.

